17.3 INFORMED CONSENT FORM (ICF)

An Informed Consent template that covers all protocol procedures and follows GCP Guidelines will be prepared by Sight Sciences and made available to each Investigator. The Investigator may adapt these templates to the requirements of the local IRB and of the institution where the study is conducted, but any revisions made to the ICF must be submitted to the sponsor for review prior to submission to the IRB. A copy of each IRB-approved ICF version is to be made available to Sight Sciences and its CRO. The approved, IRB-stamped ICF is to be kept in its full length in the study Regulatory Binder. Original, signed ICFs are to be maintained in the subject's study records and must be made available for monitoring review.

17.4 Public Listing of Study

The study will be listed on the NIH website www.clinicaltrials.gov.

18 STUDY ADMINISTRATION

18.1 DEVICE ACCOUNTABILITY

With each shipment of study devices, Sight Sciences will include a Packing List that will give the amount shipped and the lot numbers. This packing list must be reconciled by the investigational site with the contents of the shipment and then recorded on the Device Accountability Logs (these logs are contained within the regulatory binder at the site). All study products at the site must be stored in a secured/locked area. When

study devices are used, returned or disposed of, their disposition (including the disposition and date of disposition) must be recorded on the Device Accountability log.

Device reconciliation activities will also be conducted periodically in conjunction with site monitoring visits. The investigator must maintain accurate records of the receipt and disposition of all devices shipped by Sight Sciences.

18.2 Early Termination or Suspension of an Investigation

Sight Sciences may terminate the study, in which case the investigators and associated IRBs will be notified in writing. Possible reasons for study termination include but are not limited to:

- The discovery of an unexpected, significant, or unacceptable risk to the study subjects implanted with the device
- Withdrawal of FDA listing of the TearCare product.

Sight Sciences reserves the right to stop the study at a center any time after the initiation visit if there have been no subject enrollments.

Likewise, a principal investigator may terminate the study at his/her institution. This decision must be followed by written notification to Sight Sciences within five working days, stating the reasons for termination.

If the study is terminated, every effort should be made to obtain final follow-up from all subjects.

In the event that there are significant human use issues with the device, the investigator will be consulted to make a determination of whether the study should be terminated or not.

18.3 Investigator Responsibilities

18.3.1 GENERAL RESPONSIBILITIES OF INVESTIGATORS

An Investigator is responsible for ensuring that an investigation is conducted according to the signed agreement, the investigational plan and applicable FDA regulations, for protecting the rights, safety, and welfare of subjects under the Investigator's care, and for the control of devices under investigation. An Investigator also is responsible for ensuring that informed consent is obtained in accordance with 21 CFR part 50.

18.3.2 Specific Responsibilities of Investigators

- Awaiting approval An Investigator may determine whether potential subjects would be interested in participating in an investigation, but shall not request the written informed consent of any subject to participate, and shall not allow any subject to participate before obtaining IRB approval.
- 2. Subject Qualification -The Investigator is responsible for ensuring that all subjects entering the study conform to the patient selection criteria.
- Compliance An Investigator shall conduct an investigation in accordance with the signed agreement with the Sponsor, the investigational plan, all applicable FDA regulations, and any conditions of approval imposed by an IRB.

18.3.3 INVESTIGATOR RECORDS

A participating Investigator shall maintain the following accurate, complete, and current records relating to the Investigator's participation in an investigation for the period specified in Section 14.6:

- 1. All correspondence with another Investigator, an IRB, the Sponsor, a monitor, or FDA, including required reports.
- Records of each subject's case history and exposure to the device. Case histories
 include the study CRF's/worksheets and supporting data including, for example,
 signed and dated consent forms and medical records. Such records shall include:
 - a) Documents evidencing informed consent.
 - b) All relevant observations, including records concerning adverse device effects (whether anticipated or unanticipated), information and data on the condition of each subject upon entering, and during the course of, the investigation, including information about relevant previous medical history and the results of all diagnostic tests.
- 3. The protocol, with documents showing the dates and reasons for each deviation from the protocol.
- 4. Any other records that FDA requires to be maintained by regulation or by specific requirement for a category of investigations or a particular investigation.

18.3.4 Investigator Reports

An Investigator shall prepare and submit the following complete, accurate, and timely reports:

 Unanticipated Adverse Device Effects - An Investigator shall submit to the Sponsor and to the reviewing IRB a report of any unanticipated adverse device effect

CONFIDENTIAL Sight Sciences

- occurring during an investigation as soon as possible, but in no event later than 10 working days after the Investigator first learns of the effect.
- 2. Withdrawal of IRB Approval An Investigator shall report to the Sponsor, within 5 working days, a withdrawal of approval by the reviewing IRB of the Investigator's part of an investigation.
- 3. Progress An Investigator shall submit progress reports on the investigation to the Sponsor, the monitor, and the reviewing IRB at regular intervals, but in no event less often than yearly.
- 4. Deviations from the Investigational Plan An Investigator shall document and report to the Sponsor any deviation from the investigational plan.
- 5. Informed Consent If an Investigator enrolls a subject without obtaining informed consent, the Investigator shall report such use to the Sponsor and the reviewing IRB within 5 working days after the use occurs.
- 6. Final Report An Investigator shall, within 3 months after termination or completion of the investigation or the Investigator's part of the investigation, submit a final report to the Sponsor and the reviewing IRB.
- 7. Other An Investigator shall, upon request by a reviewing IRB or FDA, provide accurate, complete, and current information about any aspect of the investigation.

18.4 INVESTIGATOR AGREEMENT

The principal investigators in each center shall agree to the clinical protocol and any amendments and indicate their approval and agreement by signing and dating the cover page of the study protocol and the Investigator Responsibility Agreement.

19 Publication Policy

Sight Sciences recognizes the value of disseminating research results. It is understood that the Study is part of the Multi-Center Clinical Trial and publication of results is expected. This publications policy applies to journal articles, conference abstracts, and conference presentations (posters and slides) covering Sight Sciences-sponsored clinical studies. This policy is in addition to any arrangement contained in the Clinical Trial Agreement between Sight Sciences and the investigator.

Multi-Site Data

Clinical site investigators are encouraged to propose publications and abstracts that include clinical or research data from multiple clinical sites; such projects will be

Sight Sciences Page 54 of 84

coordinated by Sight Sciences. Authorship of papers and abstracts resulting from these projects will be determined collaboratively according to the following guidelines:

- The first author on such publications will be the person who primarily wrote the
 paper and took the lead on the research. In the case of clinical trial papers
 where all authors contributed equally, authorship order may be based on site
 enrollment or other criteria at Sight Sciences' discretion.
- Other authors include those who significantly contributed to the specific work.
- At least one person from each clinical site whose study subjects appear in the
 work will be acknowledged in the manuscript/presentation in some way, either
 as an author group member, a non-author contributor, or listed in the
 acknowledgements, depending on the particular policies of the journal or
 conference.

Single Site Data

After publication of the multi-center study results in a peer-reviewed journal, or if Sponsor has not submitted a manuscript for publication in a peer-reviewed journal within twelve (12) months after the study has been completed, whichever occurs first, Investigators may publish the results of the Study generated by the Investigator, subject to the obligations of the Clinical Trial Agreement between Sight Sciences and the Investigator, and the prior approval of Sponsor in writing.

[figure not shown]
Publications Review Policy

[figure not shown]
Investigators must submit all presentations, posters, abstracts and manuscripts pertaining to this study to Sight Sciences for review in advance of their submission. Sight Sciences conducts this review to protect its proprietary rights to information, inventions, or products developed under the Study. Please use the following guideline to determine the absolute minimum advance time for submitting an item to Sight Sciences for review:

- Presentations/Posters: 5 business days in advance of presentation
- Abstracts: 5 business days in advance of submission
- Manuscripts: 30 calendar days in advance of submission for publication

In accordance with the Clinical Trial Agreement, these items must receive written approval from Sight Sciences in order for them to be submitted or presented. If an item is not received in the timeframe listed above, approval may not be granted due to insufficient time for considered review. In addition, since most of our Clinical Trial Agreements require that Sight Sciences has 60 days to review publications, Sight Sciences reserves the rights granted in those Agreements if circumstances require a longer review.

21 APPENDIX A – METHODS FOR EXAMS, TESTS AND QUESTIONNAIRES

21.1 MEDICATIONS

When recording medications that the subject is taking, be sure to ask the subject to list any over-the-counter medications and supplements they are taking that could affect dry eye disease including, for example, cold medicines, Benadryl, fish oil supplements and Omega 3 products, retinol products, Latisse, etc.

21.2 Manifest Refraction and Visual Acuity

Masked assessment: This assessment should be performed by the masked assessor.

Best-corrected visual acuity will be measured using the ETDRS method. Subjects should undergo manifest refraction prior to the ETDRS test, with the exception of the Day 1 follow-up visit. On Day 1, subjects' best spectacle corrected visual acuity (BSCVA) (i.e., without manifest refraction) will be measured using the ETDRS method. If the subject's visual acuity has worsened by ≥ 2 lines from baseline, then manifest refraction should be performed and the ETDRS measurement should be repeated.

Manifest Refraction

Refraction will be performed by the Investigator or staff using standard clinical practice.

21.3 SLIT LAMP EXAM

[figure not shown]
Masked assessment: This assessment should be performed by the masked assessor.

A standard slit-lamp examination shall be performed including inspection of the cornea at a magnification of 10X and 16 x for the presence or active inflammation or structural change, the iris and anterior chamber for inflammation, and the eyelids for crusts, collarettes, or scales.

21.4 TEAR BREAKUP TIME (TBUT)

Masked assessment: This assessment should be performed by the masked assessor.

TBUT is an indicator of tear film instability. The Dry Eye Test (DET) method should be followed using DET test strips (Amcon Laboratories). While holding a fluorescein impregnated DET strip suspended in air, use a micropipette to apply 10uL of sterile saline onto the dyed end of the strip. Do not allow the saline to drip off and do not shake the strip. Instill the dyed tip of strip into the lower conjunctival fornix.

[figure not shown]
21.5 CORNEAL STAINING

Masked assessment: This assessment should be performed by the masked assessor.

[figure not shown]
Corneal staining should be assessed immediately following TBUT measurements (i.e. within 1-4 minutes after instillation of fluorescein dye) to assure the dye does not diffuse into stroma, blurring the discrete margin of any staining defects. A yellow Wratten filter should be used to improve any visualization of corneal staining. Grade the corneal staining using the NEI/Industry Grading System provided in Figure 4 below.

Figure 4: NEI/Industry Grading System for Corneal and Conjunctival Staining

Score each of 5 areas of the cornea and total score:

Score each of 6 areas of the conjunctiva and total score:

Add cornea and conjunctival scores for total score

21.6 CONJUNCTIVAL STAINING

Masked assessment: This assessment should be performed by the masked assessor.

21.7 SCHIRMER 1 TEST

The Schirmer 1 Test measures aqueous tear quantity and is an indication of aqueous-deficient dry eye. The Schirmer 1 test, without anesthesia, should be performed by placing the filter strip in the inferior fornix for 5 minutes. Remove the strips and measure wetting in millimeters.

21.8 Meibomian Gland Secretion Scoring

Masked assessment: This assessment should be performed by the masked assessor.

The Meibomian Gland Secretion Scoring is an assessment of the quality of the secretions produced by the meibomian glands in the lower eyelids. The Meibomian Gland Secretion Scoring should be performed using the Meibomian Gland Evaluator (TearScience, Inc.). Ensure that the instrument has been cleaned using alcohol prior to each use.

Grade the quality of secretions in the lateral, central and temporal thirds of the lower eyelids. Grade the 5 central glands in each region, for a total of 15 glands per eye.

- 0 = nothing
- 0 1 = toothpaste
- o 2 = cloudy
- o 3 = clear

From this assessment the following endpoints will be calculated:

- Total Meibomian Gland Secretion Score: Sum of the grade (0 − 3) for each of the 15 glands. Range for this score is 0-45.
- Count of the number of Meibomian glands yielding clear liquid secretions.
 Range for this count is 0-15.
- Count of the number of glands secreting any liquid (clear or cloudy). Range for this count is 0-15.

21.9 INTRAOCULAR PRESSURE

Masked assessment: This assessment should be performed by the masked assessor.

The same method of measuring intraocular pressure should be used at each visit. Intraocular pressure should be measured with a Goldmann tonometer, if available.

21.10 QUESTIONNAIRES

21.10.1 GENERAL INSTRUCTIONS FOR QUESTIONNAIRES

The subject should complete all required questionnaires at the beginning of each visit before conducting other clinical testing. The only exception to this guideline is the Discomfort/Pain Questionnaire administered on Day 0, which is completed by the subject just following the study treatment (refer to instructions provided in Sections 9.5.4 and 9.5.5).

Provide a paper copy of the questionnaires and a blue or black ink pen to the subject. Review the instructions for each questionnaire with the subject and answer any questions they have about how to complete them. Then allow the subject to complete the questionnaires on their own (i.e. self-administered).

Study staff should review the questionnaires before the subject leaves the office to check for missing or multiple answers on a given question. If these are found, please point this out to the subject and allow them to revise their response(s) to the specific question(s). Please confirm initials and date of the subject on the last page of the questionnaire. Do not allow the subject to take the questionnaires home.

21.10.2 OSDI QUESTIONNAIRE

The OSDI has 12 questions. Based on the answers provided by the subject, study staff calculate the overall OSDI Total score (from 0-100) and scores for the three subscales according to the OSDI instructions. Based on the recommended cutoffs for OSDI Total score, the severity of the subject's dry eye symptoms will be categorized as follows:

- o Normal 0-12
- o Mild 13-22
- Moderate 23-32
- o Severe 33 or higher

21.10.3 SANDE QUESTIONNAIRE AND EYE DRYNESS VAS

The SANDE is a simple dry eye instrument containing two items measuring the frequency and severity of symptoms, each is assessed on a 100 mm visual analog scale (VAS) ranging from 'Never/Very comfortable' to 'All the time/Very severe' and scored from 0 to 100. The Eye Dryness Visual Analog Scale measures subject's level of discomfort related to eye dryness ranging from "No discomfort/maximal discomfort."

Three scores will be obtained from the SANDE:

- Frequency score (ranging from 0 to 100): The distance (in mm) between the left end of the scale and the subject's response.
- Severity score (ranging from 0 to 100): The distance (in mm) between the left end of the scale and the subject's response.
- A SANDE Total score (also ranging from 0 to 100): This is calculated as the square-root of the product of the Frequency and Severity scores.

The Eye Dryness Score is derived from the Eye Dryness Visual Analog Scale. The Eye Dryness Score (ranging from 0 to 100) is the distance (in mm) between the left end of the scale and the subject's response.

Study staff should instruct subjects to record their response to each question by placing a vertical line (not an "X") across the horizontal line of the visual analog scale.

21.10.4 DISCOMFORT/PAIN QUESTIONNAIRE

The Discomfort/Pain Questionnaire is designed to assess the degree of discomfort or pain that the subject experiences during and immediately after the study treatment on

Day 0 and post-treatment (Day 1). Subjects are asked to indicate their level of discomfort and pain using a Visual Analog Scale provided in the case report forms.

22 APPENDIX B — INSTRUCTIONS FOR WARM COMPRESS AND LID MASSAGE

Perform the warm compress and lid massage at home once each day.

Instructions

1. Prepare the warm compress

- a. Using a clean wash cloth, run it under warm, shower temperature tap water to saturate it. It is important that the water be warm, or showertemperature, but not so hot that it causes pain or injury.
- b. Squeeze the wash cloth to remove excess water.
- c. Fold the washcloth in thirds.

2. Apply the Warm Compresses

- a. Test the washcloth to make sure it is not too hot. If it is too hot, wait about 10 seconds before testing again.
- b. With eyes closed, apply the warm compress over your closed eyelids for 5 minutes.

3. Lid Massage

- a. Lid massage should be performed immediately after completing the 5 minutes with the warm compress.
- b. Do not vigorously rub your eyelids. Avoid contacting or scratching your eye.
- c. To massage the upper eyelids, place one finger at the outer edge of your eyelid to hold it closed and slightly taut. Using the opposite hand, place a finger on the upper eyelid by the nose and, using mild pressure, run the finger along the lower edge of the upper eye lid toward the outside of the eye. Repeat on the opposite eye.
- d. To massage the lower eyelid, place one finger at the outer edge of your eyelid to hold it slightly taut. Look up. Using the opposite hand, please a finger on the lower eyelid by the nose and, using mild pressure, run the finger along the upper edge of the lower lid toward the outside of the eye. Repeat on the opposite side.

4. Warm Compress Log

a. Use the Warm Compress Log sheet to record the date and time that you perform the warm compress and lid massage. Bring this log with you to each follow-up visit.

23 APPENDIX C - STATISTICAL ANALYSIS PLAN

23.1 ENDPOINTS AND ANALYSIS METHODS

23.1.1 PRIMARY EFFECTIVENESS ENDPOINT

The primary effectiveness outcome is the change from baseline in Tear Break-Up Time (TBUT) at the 1 month follow up. TBUT will be analyzed using a linear mixed effects (LME) model. This will allow for the proper incorporation of within-person correlation into the statistical tests, and will also allow for adjustment for baseline measurements.

The linear mixed effects model for TBUT can be written as follows:

$$y_{ij} = \beta_0 + \beta_1 T_i + \beta_2 TBUT_{ij,0} + b_{0i} + \epsilon_{ij}$$

Where

- $TBUT_{ij,0}$ is the baseline TBUT value for subject i, eye j, week 0.
- y_{ij} is the 1 month change from baseline TBUT for subject i, eye j.

$$y_{ij} = TBUT_{ij,4} - TBUT_{ij,0}$$

- T_i is the 0,1 treatment indicator for subject i
- $\beta_0, \beta_1, and \beta_2$ are the fixed effect parameters
- b_{0i} is the random effect (random intercept term) for subject i

$$b_{0i} \sim N(0, \sigma_a^2)$$

ullet ϵ_{ii} is the normally-distributed error term

$$\epsilon_{ij} \sim N(0, \sigma_e^2)$$

• $\{b_{0i}\}$ and $\{\epsilon_{ij}\}$ are independent

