5.2.2 CLINICAL STUDY OF THE TEARCARE SYSTEM (2017)

Following completion of the design and development of the commercial version of the TearCare System, a single center pilot study was initiated to collect additional clinical data.

Objectives

The objective of this study was to evaluate the clinical utility, safety, and effectiveness of the TearCare™ System compared to standardized warm compress therapy.

Subjects

Twenty-four (24) subjects with symptoms of dry eye in the past 3 months were enrolled. The average age was 67.6 ± 13.5 years (range 29.7 - 89.8 years). All subjects were female, white and not Hispanic or Latino. All subjects had a SPEED score ≥ 6 at the Baseline visit. All subjects had a Tear Break-up Time (TBUT) of <10 seconds in at least one eye at baseline and 72% (17/24) had a Schirmer 1 score (non-anesthetized) of ≤ 10 mm in at least one eye at the Baseline visit.

Methods

This was a prospective, single-center, randomized, parallel-group, clinical trial. Subjects with DED were randomized to either a single TearCare treatment conducted at the clinic or 4 weeks of daily warm compress therapy. The TearCare procedure consisted of 12 minutes of thermal eyelid treatment immediately followed by manual expression of the meibomian glands. Warm compress therapy consisted of once daily application of the compresses to the eyelids for 5 minutes. Subjects were followed to 6 months post-treatment. The primary effectiveness endpoint was defined as change from baseline to 4 weeks for Tear Break-up Time (TBUT). Secondary effectiveness endpoints included meibomian gland assessment, corneal and conjunctival staining scores, and assessment of dry eye symptoms using validated questionnaires. Safety was evaluated by collecting device-related adverse events, intraocular pressure, and best spectacle-corrected Snellen Visual acuity.

Results

Twenty-four subjects were enrolled and completed 6 months follow-up. Data are summarized in Table 2 below.

At 1 month follow-up, TearCare subjects demonstrated an improvement from baseline in mean (\pm SD) TBUT of 11.7 \pm 2.6 seconds compared with an average worsening of -0.3 \pm 1.1 seconds for subjects in the warm compress group (p<0.0001). Significantly greater improvements in the change from baseline in meibomian gland scores, as well as corneal and conjunctival staining scores were observed in the TearCare group. Subjects

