23.2 SAMPLE SIZE CALCULATIONS

23.2.1 TEAR BREAKUP TIME

The primary Tear Breakup Time (TBUT) endpoint is measured on a per-eye basis. In order to account for the correlation between eyes the sample size is calculated in two steps. The first step is to carry out a standard sample size calculation for the number of eyes based on a two-sample t-test with unequal variances. This test is appropriate for a sample of independent eyes from the two groups, that is, a study in which only one eye per subject is enrolled. The second step is to allow for two eyes per subject by adjusting the independent sample size to account for the correlation between eyes.⁵⁷ This is done by multiplying by a "design effect" (DEFF) that can be calculated from the pilot study data (provided in Section 5.2.2). Finally we allow for some loss to follow up and then divide by 2 (eyes per subject) to arrive at a final enrolled sample size in terms of number of subjects.

[figure not shown]
This sample size calculation does not account for the adjustment for baseline TBUT in the analysis model. That adjustment should only serve to increase the power of the test, so this simpler calculation is conservative in that sense.

For the sample size calculation, a positive treatment effect for the warm compress control was assumed, reducing the TBUT time per eye by 4 seconds, with a standard deviation of 2. This is somewhat conservative based on the pilot study data (this is on the upper end of what we expect to see for the Warm Compress group).

For the TearCare device a treatment effect of 6 seconds, with standard deviation 3 was assumed. This is also somewhat conservative, as it is on the lower end of what we expect to see in the TearCare group based on the pilot study data.

[figure not shown]

Finally, we will assume that 10% of the enrolled subjects will be lost to follow-up. Based on these assumptions, Table 4 shows sample sizes for powers of 80%, 90%, and 95%.

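### The primary TBUT model assumes one variance for both arms while the sample size assumes two; this is harmless with equal arms, modestly wrong otherwise, and almost free to correct.

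*Combined protocol and SAP*

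**What the plan says.** **Analysis model.** SAP section 23.1.1 models each eye's one-month change in TBUT on treatment and baseline TBUT, with a random intercept per subject. The intercept is "b_{0i} \sim N(0, \sigma_a^2" and the residual "\epsilon_{ij} \sim N(0, \sigma_e^2" (both quotes stop before the closing bracket). Neither variance carries an arm index. The residual "is the normally-distributed error term", and nothing more is said about it.

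**Sample size.** Section 23.2.1 starts from a "two-sample t-test with unequal variances". For control it assumes an effect described as "reducing the TBUT time per eye by 4 seconds, with a standard deviation of 2" (the same sentence calls it a positive effect, and it is read that way here). For TearCare, "a treatment effect of 6 seconds, with standard deviation 3 was assumed".

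**Pilot.** Section 5.2.2 reports a one-month change in "TBUT of 11.7 \pm 2.6 seconds compared with an average worsening of -0.3 \pm 1.1 seconds" for TearCare and warm compress respectively.

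**Arm sizes.** Randomization is 1:1 in blocks of 2 or 4 (section 9.5.3), 100 per arm, with 10% dropout allowed for and no rate by arm (section 12.7). The primary population is per-protocol (section 12.2). The 3- and 6-month TBUT tests reuse the primary model (section 12.5.6).

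No visible section gives arm-specific variances, a robust variance or a check for unequal variance. The sensitivity analyses in 23.1.3 deal with missing data only.

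**The concern.** The plan expects TearCare changes to be more variable than control changes, then analyses them with a model that assumes they are not. A common-variance model averages the two variances, weighting each arm roughly by its size, whereas the true variance of a difference weights each by the inverse of its size. The two agree when the arms are equal and part company when they are not. If the more variable arm is the smaller one, the reported standard error is too small and the test rejects too often; in the reverse case it is too large. The primary population excludes subjects after randomization, so the arms analysed need not be equal even though the arms randomized nearly are. At stake is the exactness of the primary standard error, and of the 3- and 6-month ones, in a trial meant to support a change of indication.

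**Working it through.** **Inputs.** Planning SDs per eye 3 (TearCare) and 2 (control), difference 6 − 4 = 2 s, 10% loss (section 23.2.1); pilot SDs 2.6 and 1.1 (section 5.2.2). Assumed, because not visible: two-sided alpha 0.05, a design effect of 1 to 2 for two eyes, and all unequal arm sizes.

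**1. The plan's own figure.** Eyes per arm for 90% power = (1.96 + 1.28)² × (9 + 4) / 2² ≈ 34.1, so 35. Multiplying by the design effect and dividing by 0.9 and by 2 eyes gives 20 to 39 subjects per arm, 40 to 78 in total. With 90 evaluable per arm and the worst design effect of 2, the SE is sqrt(13/90) = 0.38 and the expected z is 2/0.38 = 5.3; power exceeds 99.9%. The stated power of more than 90% is reproduced with a wide margin.

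**2. Can inter-eye correlation remove the difference in variance?** The variance of a subject's two-eye mean is 9(1 + rT)/2 in TearCare and 4(1 + rC)/2 in control. For correlations between 0 and 1 the first is at least 4.5 and the second at most 4. It cannot.

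**3. SE of the treatment difference.** Reported SE² = [((nT − 1)sT² + (nC − 1)sC²)/(nT + nC − 2)] × (1/nT + 1/nC). True SE² = sT²/nT + sC²/nC. Actual test size = 2 × P(Z > 1.96 × reported SE/true SE). With equal inter-eye correlation in both arms, the factor (1 + r)/2 cancels from the ratio.

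Example, 80 v 95: the pooled variance is (79 × 9 + 94 × 4)/173 = 6.283, so reported SE² = 6.283 × 0.02303 = 0.1447. True SE² = 9/80 + 4/95 = 0.1546. The ratio of SEs is sqrt(0.1447/0.1546) = 0.967, and the test size 5.8%.

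| TearCare v control | SE ratio, SD 3 v 2 | Test size |
|---|---|---|
| 90 v 90 | 1.000 | 5.0% |
| 90 v 100 | 0.980 | 5.5% |
| 80 v 95 | 0.967 | 5.8% |
| 80 v 100 | 0.958 | 6.0% |
| 95 v 80 | 1.034 | 4.3% |
| 100 v 80 | 1.044 | 4.1% |

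With the pilot SDs, the test size is 5.9% at 90 v 100 and 6.5% at 80 v 95.

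**4. Range over inter-eye correlation at 80 v 95.** With rT = 0 and rC = 1 (variances 4.5 v 4), the ratio is 0.995 and the test size 5.1%. With rT = 1 and rC = 0 (9 v 2), they are 0.947 and 6.4%.

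**5. Simulation of the stated model** (REML, random intercept, baseline covariate, correlation assumed 0.6, 6,000 runs, Monte Carlo SE 0.3 points), SD 3 v 2: 4.8% at 90 v 90, 5.1% at 90 v 100, 5.8% at 80 v 100 and 3.8% at 100 v 80. This agrees with the formula to within simulation error.

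**6. Arm means.** At equal n the common SD is sqrt((9 + 4)/2) = 2.55. For TearCare 2.55/3 = 0.85, an SE 15% too small (a 95% interval covers about 90%). For control 2.55/2 = 1.275, an SE about 27% too large (coverage about 99%).

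**The case against.** The case against acting is strong on size. At the planned 1:1 allocation the treatment test is correct, and even 90 v 100 moves the SE by only 2%. The 80 v 95 case means 20% against 5% loss, which nothing in the plan predicts. That stands.

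A reader might infer that TearCare will be the smaller arm because only its subjects may wait up to 7 days for treatment. The documents do not support this. The wait is expressly allowed in section 9.5.1, so it is no deviation; subjects who withdraw before treatment may be replaced (section 9.9); and the named exclusions (section 9.8) apply to both arms. Control carries a daily home regimen and could lose as many, in which case the test is conservative.

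A reader might also take the arm-mean figures as errors in planned results. No visible section plans model-based intervals for arm means. Section 12.5.1 tabulates outcomes by group, where raw SDs are unaffected, and the single-arm models in 23.1.6 pool nothing across arms.

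Finally, 23.2.1 presents its formula as a simplification, and a planning formula need not share the analysis model's variance structure. This is fair: it is an inconsistency between two parts of the plan rather than a mistake in either. But the unequal SDs are the plan's stated expectation, and the pilot points the same way more strongly.

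**Conclusion.** The point holds in a limited form. The primary model imposes a common variance that the plan's own figures contradict, and no visible provision corrects for it. The primary SE and test are right when the arms are equal. They are modestly wrong when they are not: about 2% of the SE at 90 v 100 and 3.3% at 80 v 95, where test size is 5.8%, or 5.1% to 6.4% across inter-eye correlations of 0 to 1 differing by arm. The direction depends on which arm is smaller. Model-based intervals for arm means, if anyone reports them, would be too narrow for TearCare and too wide for control even with equal arms.

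The documents do not support the stronger reading that the primary test is invalid or that its result is at risk: an expected z above 5 is not sensitive to a 3% change in SE.

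The figures rest on assumed arm sizes, assumed inter-eye correlations, two-sided alpha 0.05, and SDs of raw change standing in for SDs after baseline adjustment. Low priority.

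**What to change.** In 23.1.1, state that the subject-intercept and residual variances are estimated separately by treatment arm. A subject-clustered robust variance with small-sample degrees of freedom would serve as well. Say that the 3- and 6-month TBUT tests in 12.5.6 use the same specification, since they reuse this model.

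The cost is one line of SAP text and one model option, with two extra variance parameters under the first choice. The sample size does not change. It should be done before any data are seen: a variance structure chosen afterwards would look data-driven and would have to be noted as a deviation under section 12.9.
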